5.3.1 Re-screening Activities

Subjects who initially screen fail for this study may be permitted to re-screen. Re-screening may be permitted on a case-by-case basis following PI discussion with the Medical Monitor regarding whether a subject remains potentially eligible to participate in the study. A subject who is re-screened is not required to sign another ICF if the re-screening occurs within 30 days from the previous ICF signature date. There is no minimum period of time a subject must wait to re-screen for the study. The subject must meet all eligibility criteria at the time of re-screening in order to qualify for the study. Depending on the time from last screening, the medical monitor will determine what assessments need to be repeated.

6 STUDY DRUG

6.1 Supply and Storage

Study drug formulated in hydroxypropyl methylcellulose (HPMC) capsules will be provided in bottles containing 65 capsules of 50 mg dose or 150 mg dose (based on freebase CT1812 fumarate salt) or its matching placebo. The bottles (original container) are induction sealed, child proof screw-top bottles with desiccant packs.

All study drug (unopened and opened bottles) will be stored refrigerated between 2°C to 8°C [35.6°F to 46.4°F] in their original bottles.

6.2 Packaging and Labeling

The treatment label will include a study reference code, drug identifier, quantity of dosage units, and lot number at a minimum, as well as other pertinent information according to US FDA or local regulations. The expiry or use-by date will be stored in the IRT/IVRS/IWRS or according to local regulations. Study drug should not be used after the expiry or use-by date. All packaged and labelled supplies will be formally released in accordance with both Good Manufacturing Practice (GMP) and Good Clinical Practice (GCP) guidelines.

6.3 Administration

CT1812 or matching placebo will be administered orally as a single daily dose for 6 months. All subjects will take the first dose in the clinic with food and be observed for 2 hours. A single daily dose consists of 2 capsules of study drug. Two (2) capsules to be taken with food. Daily outpatient dosing should occur in the morning (i.e., prior to 12 pm). To ensure appropriate specimen collection times relative to dosing on clinic days, subjects will be asked to bring their study medication to clinic visits and to take their medication at the clinic upon the instruction of the site staff. On "Drug Dispensation" clinic visits drug accountability will be completed for the bottle returned by the subject and the "in office dose administration" will be taken for that visit from the newly assigned bottle.

6.3.1 Safety Stopping Rules

Dosing may be terminated by the Sponsor at the recommendation of the DSMB (Drug Safety and Monitoring Board) based on safety and tolerability data, or at the discretion of the Sponsor; as a result, there are no study-specific stopping rules defined in this protocol.

The occurrence of any one of the following events will result in a review of study safety information to date by the Sponsor and DSMB.

- Two occurrences of the same or similar serious adverse event (SAE) assessed as probably or possibly related to dosing with investigational product.
- Two or more different subjects with the same or similar severe AE assessed as probably or possibly related to dosing with the investigational product.
- Four or more subjects with the same or similar moderate AE which is possibly or probably related to dosing with investigational product.

The Sponsor and DSMB will review the available safety data and recommend whether dosing should continue, or if study drug administration should be terminated, or if additional monitoring procedures or safety precautions need to be employed.

The study or a dose group may also be terminated if the Sponsor and DSMB determine that any adverse event(s) are occurring that are intolerable or pose a medically unacceptable safety risk. For individual subjects:

Any participant who develops the following liver function test (LFT) laboratory abnormalities will not receive any additional doses and will be monitored until resolution of the AE or the return of laboratory abnormality to the acceptable screening value(s)

- Elevated ALT or AST greater than 5 X Upper Limits of Normal (ULN)
- Elevated ALT or AST greater than 3 X ULN in combination with total bilirubin > 2 X ULN or INR > 1.5 X ULN
- ALT or AST > 3 X ULN with the appearance of fatigue, nausea, vomiting, right upper quadrant pain or tenderness, fever, rash, and/or eosinophilia (>5%)

Serial monitoring of ALT/AST/bilirubin and INR will be performed, initially with repeat values within 4 days of discontinuation of study drug. If LFTs are still elevated 4 days post-study drug interruption, participants should have LFTs checked again 4 days later (+/- 1 day). The site investigator and medical monitor should agree to a plan for further LFT monitoring depending on whether the LFTs are still increasing or trending towards normal. Repeat testing should be carried out until LFTs have normalized. The LFTs in this instance can also be run locally for more rapid turnaround.

In the event a reversible etiology is found to explain the elevated liver enzymes (such as a common bile duct stone), drug may be restarted following normalization of LFTs, and after discussion between the Medical Monitor and site PI.

Study drug will be temporarily discontinued if a participant does not achieve the aforementioned levels of elevated LFTs but has an elevation of ALT or AST $>3 \times$ ULN. These participants will have LFTs retested within 4 days after their last dose of study drug. If LFTs are still elevated 4 days post-study drug interruption, participants will have LFTs checked again 4 days later (± 1 day), and the site PI and medical monitor will agree to a plan for further monitoring of the findings. The LFTs in this instance can also be run locally for more rapid turnaround.

LFTs do not need to be intensively monitored when ALT and AST are $\leq 3 \times$ ULN with no elevation of bilirubin, however the investigator and the medical monitor will formulate a plan for serial testing of LFTs. Cessation of dosing is not required in this circumstance but may be temporarily interrupted at the discretion of the investigator.

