Safety Stopping Rules:

Dosing may be terminated by the Sponsor at the recommendation of the DSMB (Data and Safety Monitoring Board) based on safety and tolerability data, or at the discretion of the Sponsor; therefore, there are no study-specific stopping rules defined in this protocol.

The occurrence of any one of the following events will result in a review of study safety information to date by the Sponsor and DSMB.

Two occurrences of the same or similar serious adverse event (SAE) assessed as probably or possibly related to dosing with investigational product.

Two or more different subjects with the same or similar severe AE assessed as probably or possibly related to dosing with the investigational product.

Four or more subjects with the same or similar moderate AE which is possibly or probably related to dosing with investigational product.

The Sponsor and DSMB will review the available safety data and recommend whether dosing should continue, study drug administration should be terminated, or additional monitoring procedures or safety precautions need to be employed.

The study or a dose group may be terminated if the Sponsor and DSMB determine that any adverse event(s) are occurring that are intolerable or pose a medically unacceptable safety risk. For individual subjects:

Any participant who develops the following liver function test (LFT) laboratory abnormalities will not receive any additional doses and will be monitored until resolution of the AE or the return of laboratory abnormality to the acceptable screening value(s)

- Elevated ALT or AST greater than 5 X Upper Limits of Normal (ULN)
- Elevated ALT or AST greater than 3 X ULN in combination with total bilirubin > 2 X ULN or INR > 1.5 X ULN
- ALT or AST > 3 X ULN with the appearance of fatigue, nausea, vomiting, right upper quadrant pain or tenderness, fever, rash, and/or eosinophilia (>5%)

Serial monitoring of ALT/AST/bilirubin and INR will be performed, initially with repeat values within 4 days of discontinuation of study drug. If LFTs are still elevated 4 days post-study drug interruption, participants should have LFTs checked again 4 days later (+/- 1 day). The site investigator and medical monitor should agree to a plan for further LFT monitoring depending on whether the LFTs are still increasing or trending towards normal. Repeat testing should be carried out until LFTs have normalized. The LFTs in this instance can also be run locally for more rapid turnaround.

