12.2.2.2 Assessment of Intensity

The intensity of each AE will be rated according to the following 3-point scale:

- **Mild:** Awareness of signs or symptoms, but no disruption of usual activity.
- **Moderate:** Event sufficient to affect usual activity (disturbing).
- **Severe:** Inability to work or perform usual activities (unacceptable).

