## 4. STUDY DESIGN AND PLAN

This is a multicenter, randomized, double-blind, placebo-controlled study in subjects with mild to moderate DLB.

Subjects will be screened for eligibility by physical, laboratory, psychometric and neurologic examinations, and neuroimaging. Subjects may opt into collection of pre-dose Cerebrospinal fluid (CSF). If a subject opts into CSF collection, this is to be completed along with screening procedures  $\leq 42$  days prior to randomization at Baseline/Day 1. After having met all inclusion criteria, and none of the exclusion criteria, subjects will be randomized equally to one of 3 treatment arms (CT1812 at doses of 100 mg/day, 300 mg/day or placebo, up to n=40 group). On clinic visit days, study drug will be taken in the clinic after all baseline procedures been conducted. On days where there are no clinic visits, subjects will take study drug each morning at home. Subjects and their caregivers/ study partner will return to the clinic for repeat psychometric/neurologic testing, safety procedures and pharmacokinetic (PK) and pharmacodynamic (PD) sample collection at the intervals described below.

Subjects will return to the clinic approximately every 2 weeks after their Baseline visit until Day 70, then every 4 weeks until Day 182. A safety follow-up visit will occur approximately 28 days after the end of treatment for all subjects that complete through Day 182.

Subjects who prematurely discontinue the study for any reason will be asked to attend an early termination visit within 2 weeks of the last dose of study drug.

Dosing may be terminated by the Investigator if in the best interest of the subject, by the Sponsor at the recommendation of the Drug Safety and Monitoring Board (DSMB) based on safety and tolerability data, or at the discretion of the Sponsor; as a result, there are no study-specific stopping rules defined in the protocol.

The occurrence of any one of the following events will result in a review of study safety information to date by the Sponsor and DSMB.

- Two occurrences of the same or similar serious adverse event (SAE) assessed as probably or possibly related to dosing with investigational product.
- Two or more different subjects with the same or similar severe adverse event (AE) assessed as probably or possibly related to dosing with the investigational product.

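### Related, symptom-free permanent liver stops can accumulate without reaching any mandatory Sponsor/DSMB review trigger; a count of two such subjects should be added

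*Protocol*

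**What the plan says.** Protocol 6.3.1 sets no study-wide stopping rule but lists three events that oblige the Sponsor and DSMB to review the safety data. All three require the event to be judged possibly or probably related:

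- two occurrences of a similar serious adverse event;
- "Two or more different subjects with the same or similar severe AE assessed as probably or possibly related to dosing with the investigational product" (synopsis wording, the same in 6.3.1);
- "Four or more subjects with the same or similar moderate AE which is possibly or probably related to dosing with investigational product".

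SAP 4 restates the list, for example "Two or more different subjects with the same or similar severe adverse event (AE) assessed as probably or possibly related".

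The same section sets permanent liver stops for individual subjects. Two need no symptom: ALT or AST above 5 x ULN, and "Elevated ALT or AST greater than 3 X ULN in combination with total bilirubin > 2 X ULN or INR > 1.5 X ULN". The third is ALT or AST above 3 x ULN with symptoms, rash, fever or eosinophilia. A lesser rule covers isolated values above 3 x ULN: "Study drug will be temporarily discontinued if a participant does not achieve the aforementioned levels of elevated LFTs".

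Protocol 12.2.2.2 grades intensity on three levels. Mild is "Awareness of signs or symptoms, but no disruption of usual activity"; moderate and severe both require an effect on usual activity. Protocol 12.2.1 makes a clinically significant laboratory abnormality an adverse event but gives it no grade. Protocol 13.1 names no liver value as serious and leaves important medical events to judgement.

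**The concern.** Liver tests are the only laboratory findings for which 6.3.1 sets individual stopping thresholds. The rule that ends one subject's dosing is a laboratory value. The rule that compels a look across subjects is a clinical grade. Nothing connects the two. Whether several related liver stops force a review therefore depends on how each investigator grades a value the subject cannot feel.

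Subjects who meet the criteria are protected, because they stop dosing. What is at stake is the timing of a cross-subject review while other subjects continue on drug, in a trial whose primary objective is safety and tolerability.

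**Working it through.** **1. Can a permanent liver stop miss every trigger?** Setting the 6.3.1 criteria beside 12.2.2.2 and 13.1:

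| Permanent-stop criterion | Symptom needed? | Routes to a trigger |
|---|---|---|
| ALT/AST >5 x ULN | No | Only if graded above mild, or judged an important medical event |
| ALT/AST >3 x ULN with bilirubin >2 x ULN or INR >1.5 x ULN | No | The same, but with raised bilirubin an important-medical-event judgement is readily made |
| ALT/AST >3 x ULN with symptoms, rash, fever or eosinophilia | Yes, unless eosinophilia is the only finding | Symptoms may support moderate or severe |

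A symptom-free value does not disturb usual activity, so mild is its nearest grade. Mild, non-serious events appear in none of the three triggers, at any count. The gap lies mainly in the first row.

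**2. How long could a review be delayed?** Protocol 12.1 gives the DSMB data quarterly: 365.25 / 4 = 91 days. That is the longest wait for the next data package, if the second stop falls just after the previous one and no ad hoc meeting is called. If the second stop falls at random within a quarter, the average wait is about half of that, roughly 46 days.

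**3. How often would each count be reached?** The plan states no operating characteristics for the triggers, so there is no figure of its own to reproduce. Active subjects: 120 x 2/3 = 80. The documents give no rate of permanent stops, so the rate p is an assumption, taken from 1% to 10%. With X binomial(n, p):

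P(X ≥ 2) = 1 − (1−p)^n − n p (1−p)^(n−1)

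For n = 80, p = 0.02: 1 − 0.199 − 0.324 = 0.477. P(X ≥ 4) is the corresponding upper tail. When only half the events are graded moderate, p is halved.

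| Assumed p | Two stops | Four, all graded moderate | Four, half moderate and half mild | All mild |
|---|---|---|---|---|
| 1% | 0.191 | 0.009 | 0.001 | 0 |
| 2% | 0.477 | 0.077 | 0.009 | 0 |
| 5% | 0.914 | 0.572 | 0.141 | 0 |
| 10% | 0.998 | 0.965 | 0.572 | 0 |

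All columns after the second assume the events are judged non-serious and none is graded severe. These are probabilities that a trigger fires at some time in the trial. They do not measure benefit, because the DSMB sees the data each quarter in any case. The benefit is bounded by step 2.

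**4. How often would the added count prompt an unnecessary review?** Suppose the drug has no liver effect and a proportion p of all 120 subjects (assumed) meet a criterion from background causes and are called related. For p = 1%: 1 − 0.299 − 0.363 = 0.338.

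| Assumed p | P(at least two of 120) |
|---|---|
| 0.25% | 0.037 |
| 0.5% | 0.122 |
| 1% | 0.338 |

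**The case against.** The strongest reply is that discretionary oversight is the declared design. Section 6.3.1 lets the Sponsor and DSMB end the study or a dose group for any event they find unacceptable, with no grade or count. The three triggers are minimum prompts.

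The backstops are also substantial and partly liver-specific:

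- Table 1 schedules chemistry at every visit.
- Section 12.1.4 repeats ALT or AST at 2 x ULN as an unscheduled visit.
- After a stop, serial testing follows and, if values remain elevated, "The site investigator and medical monitor should agree to a plan for further LFT monitoring".
- Safety data are reviewed biweekly by the study clinician and medical monitor, and ad hoc DSMB meetings are provided for (12.1).

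A long delay therefore needs a medical monitor who knows of two related permanent stops and escalates neither. Two cases judged important medical events would already fire the first trigger. This stands: it limits the consequence to timing. It does not supply a fixed count.

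A reader might infer from Protocol 3.3 that the gap has already been seen with this drug, because two subjects in the PET study were withdrawn for liver-test increases graded mild and probably related. The documents do not support that. The enzyme levels and arms of those two are not given. The one quantified elevation above 3 x ULN was 4.7 x ULN at 560 mg, below the 5 x ULN line and at a dose above this trial's maximum. The record shows only that liver events ending treatment have been graded mild.

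Two further objections stand in part. The proposed count includes the symptomatic criterion, where grading may already work, so it is somewhat wider than the gap. And the DSMB charter, which may already set a liver count, is not among the documents.

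**Conclusion.** The point holds as a gap in the mandatory triggers. Related, symptom-free permanent liver stops, chiefly isolated ALT/AST above 5 x ULN, can be graded mild, judged non-serious and compel no review. The size is a cross-subject review up to about 91 days later than a fixed count would prompt, and only if nobody calls an ad hoc meeting.

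A reader might go further and conclude that liver signals could go unreviewed in this trial. The documents do not support this, because quarterly DSMB data and biweekly review apply whatever the grade. Nor should the differences between columns in the trigger table be read as harm avoided; they depend on assumed rates and describe only whether a trigger fires.

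The conclusion about the text rests on no assumed rate. Confidence that the change would matter in practice is moderate, since it depends on investigators' grading and on an unseen charter. It is a worthwhile, low-urgency improvement.

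**What to change.** Add a fourth trigger to Protocol 6.3.1 and the synopsis: two or more subjects who meet a permanent-stop LFT criterion, assessed as possibly or probably related, prompt a Sponsor/DSMB review whatever the recorded intensity or seriousness. Temporary holds for an isolated value above 3 x ULN would not count. Two is the protocol's own count for severe events; the DSMB may choose another. If its charter already has a liver count, 6.3.1 should cite it instead. SAP 4 only restates the triggers and can be aligned at its next version.

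The text is one sentence, with no change to treatment or endpoints. Under 16.1.1 it is probably a substantial amendment needing regulatory and IRB approval, so it should be bundled with another amendment. The running cost is an occasional unnecessary review, as in step 4 of the working. Relatedness remains an investigator's judgement, so the rule narrows the dependence on judgement without removing it.

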12 SAFETY ASSESSMENTS

12.1 Assessment of Safety

A DSMB (Drug Safety and Monitoring Board) will oversee the safety of the trial. This committee will include independent experts, including an independent statistician. Safety data will be provided to the DSMB at quarterly intervals during the trial. The study clinician and study medical monitor will review trial safety data biweekly and more frequently as the safety data warrant. Similarly, more frequent ad hoc meetings of the DSMB will occur if ongoing safety data indicate interim meetings are indicated.

EVALUATION CRITERIA:

The DSMB will review the safety and tolerability of CT1812 of the subjects enrolled in the study. They may also recommend monitoring and reporting of additional safety and/or tolerability measures such as:

- Adverse events.
- Serious Adverse Events.
- Physical and neurological examinations.
- Vital signs - body temperature, systolic and diastolic blood pressure, pulse rate and respiration rate.
- Electrocardiogram (ECG).
- Clinical laboratory tests: hematology, biochemistry, coagulation, serology and urinalysis.
- Columbia Suicide Severity Rating Scale (C-SSRS).

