12.2.2 Collection and Rating of Adverse Events

During the course of the study (i.e., from the signing of the ICF through the Follow-up Visit) all AEs, irrespective of the relatedness to the study drug, will be collected and reported on the Adverse Event Report Form. The seriousness criteria should not be confused with the intensity of the event. In case of an SAE, a Serious Adverse Event Report Form must be completed and transmitted to the Sponsor or designee.

Overdoses and medication errors in the presence of clinical consequences should be recorded as AEs. The clinical consequence should be reported as “[enter AE] due to overdose”.

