  - Subjects experiencing a TEAE related to investigational product leading to discontinuation of investigational product and the total number of TEAEs related to investigational product leading to discontinuation of investigational product

- Subjects experiencing a TEAE leading to discontinuation of study and the total number of TEAEs leading to discontinuation of study
- Subjects experiencing a TEAE related to investigational product leading to discontinuation of study and the total number of TEAEs related to investigational product leading to discontinuation of study

In addition to the overall TEAE summary the following summaries will be presented.

- Subject incidence of TEAEs and total number of unique TEAEs by MedDRA SOC and PT
- Subject incidence of TEAEs by MedDRA SOC, PT, and highest severity. At each level of subject summarization, a subject is classified according to the highest severity if the subject reported 1 or more events. AEs with missing severity will be considered severe for this summary.
- Subject incidence of TEAEs by MedDRA SOC, PT, and maximum relationship to study drug (related/not related). Related AEs are those reported as “Probable” or “Possible,” and unrelated AEs are those reported as “Unlikely” or “Not Related.” At each level of subject summarization, a subject is classified according to the maximum relationship if the subject reported 1 or more events. AEs with a missing relationship will be considered related for this summary.
- Subject incidence of serious TEAEs and total number of unique serious TEAEs by MedDRA SOC and PT
- Subject incidence of TEAEs leading to death by MedDRA SOC and PT
- Subject incidence of TEAEs leading to discontinuation of investigational product by MedDRA SOC and PT
- Subject incidence of TEAEs leading to discontinuation of study by MedDRA SOC and PT
- Subject incidence of non-serious TEAEs and total number of unique non-serious TEAEs by MedDRA SOC and PT

Separate listings of treatment-emergent AEs, treatment-emergent SAEs, AEs leading to death, and AEs leading to investigational product discontinuation will be presented.

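### Read literally, the DSMB review triggers fire on four moderate related cases but not on three moderate plus one severe

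*Protocol*

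**What the plan says.** Protocol 6.3.1 (Safety Stopping Rules) sets no study-specific stopping rule. It names three events, each of which is enough on its own to bring about a Sponsor and DSMB review:

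1. Seriousness: "Two occurrences of the same or similar serious adverse event (SAE) assessed as probably or possibly related to dosing with investigational product".
2. Severe intensity: "Two or more different subjects with the same or similar severe AE assessed as probably or possibly related to dosing with the investigational product".
3. Moderate intensity: "Four or more subjects with the same or similar moderate AE which is possibly or probably related to dosing with investigational product".

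The synopsis and SAP Section 4 carry the same three triggers.

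Two other parts of the protocol fix what the words mean. Section 12.2.2.2 makes moderate and severe separate grades: "The intensity of each AE will be rated according to the following 3-point scale". Section 12.2.2 keeps seriousness apart from intensity: "The seriousness criteria should not be confused with the intensity of the event". A severe AE therefore need not be an SAE, and an SAE need not be severe. No part of either document says that the moderate count includes worse grades.

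**The concern.** A safety trigger should never become less sensitive when the same set of cases gets worse. Here the second and third triggers each count one grade only. Raising one subject in a cluster from moderate to severe takes that subject out of the moderate count, and one case alone does not reach the severe threshold. A cluster that would have gone to the DSMB automatically can then fall below every threshold.

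What is at stake is the timing of an automatic review. The triggers start a review; they do not stop dosing. They matter because safety and tolerability is the primary objective, and because these three bullets are the only count-based route to a study-level review that the protocol defines.

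**Working it through.** The plan states no operating characteristic for these triggers, so there is no figure to reproduce. The check is a matter of logic and enumeration.

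**Inputs.** The three thresholds come from Protocol 6.3.1. The separation of grades comes from 12.2.2.2, and the separation of seriousness from intensity comes from 12.2.2. Assumption: each subject counts once, at one intensity.

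**Notation.** For one type of related AE, let *m* be the number of subjects rated moderate, *s* the number rated severe and *e* the number of SAE occurrences.

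- Current rule: review if *e* ≥ 2, or *s* ≥ 2, or *m* ≥ 4.
- Revised rule: review if *e* ≥ 2, or *s* ≥ 2, or *m* + *s* ≥ 4.

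**Key configurations.**

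| *m* | *s* | *e* | Current rule | Revised rule |
|---|---|---|---|---|
| 4 | 0 | 0 | review | review |
| 3 | 1 | 0 | **none** | review |
| 3 | 1 | 1 | **none** | review |
| 3 | 1 | 2 | review (SAE trigger) | review |
| 2 | 2 | 0 | review (severe trigger) | review |
| 3 | 0 | 0 | none | none |
| 3 | 0 | 1 | none | none |

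**Why this is the only gap.** A cluster missed now but caught by the revised rule must satisfy *m* ≤ 3, *s* ≤ 1, *e* ≤ 1 and *m* + *s* ≥ 4. The first, second and last conditions leave only *m* = 3 and *s* = 1, with at most one SAE. Enumerating *m* and *s* from 0 to 8 gave the same answer: the two rules differ only at (3,1,0) and (3,1,1).

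**Crossing seriousness with intensity.** Allowing mild serious events as well, the missed configuration splits into four patterns:

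- three moderate and one severe, none serious;
- the same, with one of the moderate cases serious;
- the same, with the severe case serious;
- three moderate and one severe, none of them serious, plus a separate mild SAE in a fifth subject.

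**Monotonicity.** Raise one subject's intensity by one step and leave seriousness unchanged. Under the current rule four such steps turn a review off, all of them going from four moderate to three moderate plus one severe. Under the revised rule none does. No pattern that fires now is lost.

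**How long the gap lasts.** One more moderate case gives *m* = 4 and meets the third trigger. One more severe case gives *s* = 2 and meets the second. Failing both, the next quarterly data delivery reaches the DSMB. Taking a quarter as 13 weeks and biweekly as every two weeks, 13 / 2 = 6.5, so about six medical-monitor reviews fall in that interval.

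No probability is attached to the configuration. The documents give no rates of severity or seriousness for this population.

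**The case against.** **The counting rule is assumed.** SAP 15.1 says that "a subject is classified according to the highest severity if the subject reported 1 or more events", but that governs the severity tables and not live monitoring. A subject with separate moderate and severe records of the same event could count under both triggers, and then the gap does not arise. A committee might also read moderate as at least moderate. Both points are fair. Neither reading is written down, however, and the one stated convention produces the gap. If the wider reading is what was meant, the edit simply records it.

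**Other oversight continues.** Protocol 12.1 provides that "The study clinician and study medical monitor will review trial safety data biweekly and more frequently as the safety data warrant" and that "Safety data will be provided to the DSMB at quarterly intervals during the trial". It also allows ad hoc DSMB meetings, as does SAP 10.5. SAEs must be reported within 24 hours (13.1.1), liver enzyme elevations have their own per-subject dosing rules (6.3.1), and a dose group can be terminated without any count being reached. This stands, and it limits the harm to a delay. It does not repair the rule: none of these provisions forces a DSMB review at this count, and SAE reporting does not reach a severe event that is not serious.

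**The pattern should be uncommon.** Protocol 3.3 reports one severe AE, judged unrelated, among more than 60 healthy volunteers. It reports only mild or moderate AEs in 19 subjects with Alzheimer's disease dosed for 28 days, and no drug-related SAE among 62 randomized in the ongoing six-month Alzheimer's study at the same doses. This stands as a qualitative point. These are other populations, and the first two studies had shorter dosing, so they do not supply a rate for this trial.

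**The amendment may not be trivial.** Under Protocol 16.1.1 a change that affects subject safety is a substantial amendment and needs regulatory and IRB approval, here for up to about 30 sites. That is a real but modest cost.

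**Conclusion.** The concern holds on the literal text. A stated rule gives a less protective result for a worse pattern, which goes beyond a missing detail. Its extent is one configuration per type of AE: three moderate plus one severe related case with at most one SAE. The delay lasts at most until the next moderate-or-worse related case of the same event, or until the next quarterly DSMB delivery, whichever comes first. No endpoint, estimate or error rate is affected.

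The conclusion rests on counting each subject once at a single intensity, and on moderate meaning moderate only. The first is not specified for the triggers; the second is the plain wording. The rule should be corrected, but the flaw does not leave subjects unmonitored.

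**What to change.** In the third bullet of Protocol 6.3.1 and of the synopsis, count subjects with the same or a similar related AE *of moderate or greater intensity*, keeping the threshold at four. Make the same change in SAP Section 4. Leave the first two bullets as they are.

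The edit is a few words in three places. Sample size, significance level and blinding are untouched. The costs are a protocol amendment, probably a substantial one, and an occasional additional review by the existing committee.
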